### **9.3. Subject Withdrawal Criteria**

#### **9.3.1. Discontinuation from Trial Treatment**

Subjects may be discontinued from treatment and assessments at any time, if deemed necessary by the investigator.

Potential reasons for discontinuation of treatment are:

- Lack of efficacy/worsening of disease
- Unacceptable AE
- Serious hypersensitivity reaction
- Pregnancy

Those who discontinue treatment will not automatically be withdrawn from the trial but will be encouraged to continue to follow the same visit schedule. For example: if treatment is discontinued at Week 4 (Visit 3) the subject will be encouraged to attend the remaining visits.

The reason and date the subject is discontinued from treatment will be documented in the electronic case report form (eCRF).

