#### **9.3.2. Withdrawal from the Trial**

Subjects are free to discontinue their participation in the trial at any time. Withdrawal from the trial will not affect or prejudice the subject's further care or treatment. Potential reasons for withdrawal of subjects from the trial are:

- Screening failure
- The decision of a subject to withdraw from the trial (including if the subject withdraws informed consent)
- Unacceptable treatment response
- Unacceptable adverse event
- Subject is lost to Follow-up
- Other reason(s) (e.g incorrect enrollment)

The reason and date the subject is withdrawn from the trial will be documented in the eCRF (e.g. lost to follow-up, consent withdrawn, incorrect enrolment, AEs, etc.). If a subject is withdrawn from the trial, the investigator should attempt to complete all required trial assessments (such as those at Week 48 if withdrawn during the treatment period).

All AEs should be followed-up according to Section [12.15](#).

If a subject is withdrawn from the trial, all data collected until the time of withdrawal will be used in the data presentations unless consent to use the data was withdrawn by the subject.

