2. PROJECT OVERVIEW

2.1 Study Design

This is an open-label, non-controlled, multicentre, pilot clinical trial of inhaled molgramostim in subjects with persistent pulmonary NTM infection.

The study will comprise a Screening Visit, Baseline Visit, a 48-week treatment period and a 12-week follow up period. The Screening Visit (Visit 1) will be conducted up to 10 weeks prior to the Baseline Visit (Visit 2) to determine eligibility. Adult subjects with a history of chronic NTM infection with at least 2 positive cultures in the prior two years, of which at least one is within the last 6 months prior to Screening, will be considered for enrolment. Subjects should provide a positive NTM sputum culture at Screening to be eligible.

The study will include 30 subjects.

The treatment period will consist of 14 trial visits (Screening, Baseline, and at Weeks 4, 8, 12, 16, 20, 24, 28, 32, 36, 40, 44, and 48; Visits 1-14) and a follow-up visit (Visit 15) 12 weeks after end of treatment. The visits at Weeks 28, 36 and 44 (Visits 9, 11 and 13) will include a telephone contact, all other visits will include a clinic visit.

At the Baseline Visit (Visit 2), eligible subjects will start treatment with inhaled molgramostim administered via the PARI eFlow nebulizer.

At each visit (Visits 1-15), sputum samples for staining and microscopy, and microbiological culture will be collected. If required, induced sputum may be obtained according to local standards. On the days of clinic visits (Visits 1, 2, 3, 4, 5, 6, 7, 8, 10, 12, 14 and 15), subjects will be asked to collect two additional sputum samples at home, preferably on the consecutive days after the site visit (At the commencement of the study, only 1 sample was required for Visits 2 to 7, with the additional sampling added in protocol amendment(s)). On the days of the telephone contact visits (Visits 9, 11 and 13), three sputum samples will be collected at home, preferably on consecutive days.

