9.2 Variables

9.2.1 *Primary Endpoint Variables*

- Sputum culture conversion during the treatment period defined as all available samples from three consecutive visits to be negative
- The time of culture conversion: Defined as the time the first of three consecutive visits with 100% negative samples was obtained. Subjects with no conversion will be censored at the date of their last visit.

9.2.2 *Secondary Endpoint Variables*

- Sputum smear conversion: Defined as at least three consecutive visits with 100% negative AFB stained sputum smears on microscopy during the treatment period in subjects that were smear positive at Baseline.
- Durability of sputum culture conversion: Defined as conversion at or before Week 48 and culture still negative at 12-weeks follow-up (with no positives in between).
- Durability of sputum smear conversion: Defined as conversion at or before Week 48 and smear still negative at 12-weeks follow-up (with no positives in between).
- Change from baseline in semi-quantitative grade of number of NTM on microscopy of AFB stained sputum smears
- Change from baseline in semi-quantitative grade of sputum cultures (measured by time to positivity and exploratory quantitation of cultures)
- Change from baseline in symptom scores
 - Lower Respiratory Tract Infections – Visual Analogue Score (LRTI-VAS)
 - Quality of Life Questionnaire – Bronchiectasis (QOL-B)
- Change from baseline in Global Rating of Health (GRH)
- Change from baseline in body weight
- Change from baseline in 6MWD, oxygen desaturation and Borg CR10 scores

9.3 **Biostatistical methods**

9.3.1 *Primary Endpoint*

9.3.1.1 *Sputum Culture Conversion*

Sputum culture conversion data will be listed, including time of culture conversion.

Sputum culture conversion rates (number of subjects who convert to negative out of the number per group) will be presented with 95% exact binomial confidence intervals.

On the basis of the poor historical success rates of current standard therapy, a 30% response rate for the primary endpoint will be considered clinically relevant.

Time to culture conversion will be evaluated using Kaplan Meier estimates, with 95% confidence intervals.

9.3.1.2 *Sensitivity Analyses*

In a sensitivity analysis, culture conversion will be re-defined as requiring at least 2 samples are available from each of the three consecutive visits. Sputum culture conversion rates and time to culture conversion will be analysed as part of this sensitivity analysis.

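### The Kaplan-Meier analysis of time to conversion censors deaths and outcome-related withdrawals, so it can show a more favourable figure than the primary conversion rate for the same subjects

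*SAP*

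**What the plan says.** SAP 9.2.1 dates conversion from the start of the qualifying run: "Defined as the time the first of three consecutive visits with 100% negative samples was obtained". For everyone else, "Subjects with no conversion will be censored at the date of their last visit". SAP 9.3.1.1 then states: "Time to culture conversion will be evaluated using Kaplan Meier estimates, with 95% confidence intervals". Neither section separates death or the reason for leaving from administrative censoring. Deaths appear only in a listing (SAP 10.3), and missing data are not imputed (SAP 12).

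The primary result in SAP 9.3.1.1 is a proportion, "Sputum culture conversion rates (number of subjects who convert to negative out of the number per group", with an exact binomial interval. The benchmark belongs to that rate: "a 30% response rate for the primary endpoint will be considered clinically relevant".

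Protocol 9.3.2 includes "Unacceptable treatment response" and intolerable adverse events among the reasons for leaving the trial. Protocol 9.3.1 gives "Lack of efficacy/worsening of disease" as a reason for stopping treatment. It lets the investigator stop assessments as well, but it encourages subjects who stop treatment to keep attending visits.

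The sensitivity analysis (SAP 9.3.1.2) changes only how many samples each visit must supply. Smear conversion (SAP 9.3.2.1 and 9.3.2.2) follows the same approach.

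**The concern.** Kaplan-Meier treats a censored subject as one who would go on to convert at the rate of those still followed. That cannot be true of someone who has died, and it is doubtful for someone who left because treatment was failing. The binomial rate counts these same people as non-converters. The plan therefore has two results for its primary endpoint that make opposite assumptions about the same subjects, and it does not say so. The time-to-conversion curve rises as failures leave, which is an awkward property in an open-label, single-arm pilot meant to inform later phase II work (Protocol 6.3). For smear conversion only subjects who were smear positive at Baseline count, so each leaver weighs more.

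**Working it through.** **Inputs.** From the documents: "The study will include 30 subjects" (SAP 2.1); 4-weekly visits to Week 48; a three-visit rule, so the latest possible conversion date is Week 40; censoring at the last visit. The documents give no exit rate, death rate or expected time to conversion, so there is no planned figure to reproduce. Exit rates and timings below are assumptions.

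**1. Worked case, n = 30.** Suppose 4 subjects convert early, then 6 leave as failures, then 4 of the remaining 20 convert, and all others are followed to the end.

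- Observed rate: 8/30 = 26.7% (exact 95% CI 12.3% to 45.9%).
- SAP rule: 1-KM = 1 - (26/30) × (16/20) = 30.7%.
- Aalen-Johansen, leavers as competing events: 4/30 + (20/30) × (4/20) = 26.7%.

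Kaplan-Meier hands the leavers' weight to the 20 who remain. Each then counts (26/30)/20 = 4.33% instead of 1/30 = 3.33%, and four later conversions at one extra point each make up the 4-point gap. With five leavers instead of six, 1-KM = 1 - (26/30) × (17/21) = 29.8%.

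**2. Average size, moderate assumptions.** Simulation with n = 30, true conversion 25%, onset spread over Weeks 4-40, three-visit confirmation, and leavers who never convert and exit in Weeks 4-44.

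| Share of non-converters leaving | Mean 1-KM | Excess over 25% (points) |
|---|---|---|
| 10% | 25.8% | 0.8 |
| 20% | 26.8% | 1.8 |
| 30% | 28.1% | 3.1 |
| 40% | 29.3% | 4.3 |

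**3. Near-worst case.** True conversion 30%, with 10%, 20% and 30% of *all* subjects leaving and none of them converting. Mean 1-KM is about 32.5%, 35.5% and 39% if exits fall in Weeks 4-24, and about 31.5%, 33% and 35% if they are spread over Weeks 4-44. At 30% leaving the excess is about 5 to 9 points. That setting means 0.30/0.70 = 43% of non-converters leave. At 5% leaving, the relative bias is only 2-4%.

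**4. Leaving unrelated to outcome.** With n = 30, true conversion 25% and 20-30% leaving, mean 1-KM is 24.1% to 23.7%. It is not overstated, and it is nearer the truth than the observed rate (22.0% to 20.7%).

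**5. Effect of planned Week 24 ends.** Take the worked case, but let 6 more subjects end at Week 24 before the last 4 conversions, which leaves 14 at risk.

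- Plain 1-KM: 1 - (26/30) × (10/14) = 38.1%.
- Aalen-Johansen, with Week 24 ends censored: 4/30 + (20/30) × (4/14) = 32.4%.
- Leavers kept at risk to Week 48 as non-converters: 1 - (26/30) × (16/20) = 30.7%.
- Observed: 26.7%.

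The competing-event method removes the part due to leavers, but it need not equal the observed rate once others are censored early.

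**The case against.** The strongest reply is that nothing decisive hangs on this curve. The trial is descriptive and exploratory, with no formal sample size and no decision rule, and the binomial rate beside the curve already counts leavers as failures. A reader might infer that the censoring rule could carry the trial past its 30% benchmark. The documents do not support that, because 30% is tied to the response rate and never to the Kaplan-Meier estimate. Even a reader who misapplied it would seldom see the two figures fall on opposite sides. In the step 2 simulation, 1-KM was at least 30% while the observed rate was below 30% in 0.2% and 2.1% of trials at 10% and 20% leaving, and in 7.6% and 11.8% at 30% and 40%.

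A reader might also take the 10-30% discontinuation figure in Protocol 6.2 as an exit rate for this trial. It describes stopping antibiotics because of adverse effects, not leaving a trial of inhaled molgramostim. Subjects who stop treatment but keep attending are not censored early at all. Expected deaths are also limited, since concurrent disease with a life expectancy under 6 months is an exclusion.

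Finally, the direction is conditional. Subjects who leave for an adverse event need not be poor responders. Leavers also stay in the risk set at their last visits, when a three-visit run can no longer be completed, and this pulls 1-KM slightly down.

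All of this stands, and it limits the size and consequence of the point. It does not justify treating a death, or a withdrawal for treatment failure, as uninformative censoring in a planned result.

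**Conclusion.** The point holds as a cheap improvement to a planned result, not as a threat to the primary result. As written, the SAP makes 1-KM exceed the real cumulative conversion whenever conversions follow a death, and whenever subjects who leave for poor response or an adverse event are less likely to convert than those who stay. The second condition is plausible but assumed. The likely excess is about 1 to 4 points if 10-40% of non-converters leave, rising to 5 to 9 points in the near-worst case, and it is zero if leaving is unrelated to outcome. The consequence is a second, more favourable number for the same endpoint, repeated for smear conversion and in the sensitivity analyses. The binomial rate, its exact interval and the 30% mark do not change.

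**What to change.** In SAP 9.2.1 and 9.3.1.1:

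- Make the main time-to-conversion result the Aalen-Johansen cumulative incidence of conversion with a 95% CI. Treat death, and recorded withdrawal from the trial for poor response, worsening or an adverse event, as competing events.
- Keep censoring for planned ends at Week 24 and for losses unrelated to outcome.
- Keep the Kaplan-Meier curve as supportive, labelled as the hypothetical conversion had nobody left.
- Apply the same rule to smear conversion and to both sensitivity analyses.
- State that 30% is judged on the binomial rate only.

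Keeping leavers at risk to Week 48 as non-converters is a tempting shortcut. It is not the same estimator when others are censored at Week 24 (30.7% against 32.4% in step 5). The SAP should name one method and should not promise that it will match the observed rate.

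The cost is a few lines of SAP text and code. Reasons for stopping treatment and for ending participation are already recorded in the eCRF (Protocol 9.3.1 and 9.3.2) and listed (SAP 6). The downsides are a slightly less favourable cumulative figure and reliance on the recorded reason for withdrawal, so the mapping of reasons to competing events should be fixed before the final analysis.

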Microbiology analysis of samples from UK sites will be analysed and reported by Royal Brompton Hospital (RBH) as specified in the RBH Data Transfer Specification. Data transfers are being processed on a monthly basis throughout the study, with each transfer being reconciled against the CRF data.

The final data transfer will be incorporated into the End of Study analysis once the final transfer has been received, reconciled and any issues are considered resolved.

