9.3.2 *Secondary Endpoints*

9.3.2.1 *Sputum Smear Conversion (Primary)*

Sputum smear conversion will be evaluated and presented in the same way as the primary endpoint for culture conversion.

9.3.2.2 *Sputum Smear Conversion (Sensitivity)*

In a sensitivity analysis, smear conversion will be re-defined as requiring at least 2 samples are available from each of the three consecutive visits. Sputum smear conversion rates and time to smear conversion will be analysed as part of this sensitivity analysis.

9.3.2.3 *Mycobacterial Microscopy Grading*

Mycobacterial microscopy data will be listed for each sample, including AFB positivity and AFB semi-quantitative grading. The listing will also include the overall visit AFB positivity and grading statuses. Laboratory grading terminology will be re-named as detailed in Table 4.

Table 4: *Mycobacterial Microscopy Grading*

SNP	RBH	Cross-Tabulation
No acid fast bacilli seen	No AFB Seen	Negative
Acid fast bacilli – occasional	Scanty AFB Seen +/-	Scant
Acid fast bacilli +	Moderate AFB Seen 1+	1+
Acid fast bacilli ++	Moderate AFB Seen 2+	2+
Acid fast bacilli +++	AFB Seen 3+	3+
Acid fast bacilli ++++		4+

The number of subjects who decrease over the scale (and proportion out of the number per group) will be presented with 95% exact binomial confidence intervals.

A summary table will present continuous descriptive statistics of grade for each scheduled visit.

9.3.2.4 *Mycobacterial Culture Grading*

Mycobacterial culture data will be listed for each sample, including culture positivity, culture semi-quantitative grading, time to detection in liquid media (MGIT) and organisms isolated. The listing will also include the overall visit AFB positivity and grading statuses.

The following is noted:

- MGIT and semi-quantitative grading will need to be extracted from the Comment column in the SNP data transfer.
- Semi-quantitative grading is not available for mycobacterial culture data from RBH.

For each scheduled visit, the number of subjects (and proportion out of the number per group) who report a decreased culture grade compared to Baseline will be presented with 95% exact binomial confidence intervals. Where multiple samples were taken at a visit, the worst grade will be used for comparison to Baseline.

A figure will present the mean change from baseline of semi-quantitative sputum culture grades, with error bars representing the standard deviation.

9.3.2.5 *Symptom Scores*

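### The culture-grade decrease is taken out of the whole group although UK samples have no culture grade, and time to positivity is named as the measure but only listed.

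*SAP*

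**What the plan says.** The endpoint in protocol 7.3.1.2 and SAP 9.1.2 is the change in semi-quantitative grade of sputum cultures from Baseline. SAP 9.2.2 adds how it is obtained: "measured by time to positivity and exploratory quantitation of cultures".

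SAP 9.3.2.4 gives the analysis.

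- **Listing:** "Mycobacterial culture data will be listed for each sample, including culture positivity, culture semi-quantitative grading, time to detection in liquid media (MGIT) and organisms isolated".
- **Source of the values:** "MGIT and semi-quantitative grading will need to be extracted from the Comment column in the SNP data transfer". SNP is the Australian laboratory.
- **UK laboratory:** "Semi-quantitative grading is not available for mycobacterial culture data from RBH". SAP 3.2.2.4 says of this laboratory: "Microbiology analysis of samples from UK sites will be analysed and reported by Royal Brompton Hospital (RBH").
- **Table, by visit:** "the number of subjects (and proportion out of the number per group) who report a decreased culture grade compared to Baseline", with exact binomial 95% intervals.
- **Figure:** "A figure will present the mean change from baseline of semi-quantitative sputum culture grades, with error bars representing the standard deviation".

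Two general rules also bear on the point. SAP 3.1 bases percentages on subjects with non-missing data, but only where nothing else is specified. SAP 12 reports observed data without imputation.

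**The concern.** There are two separate gaps.

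The first is the denominator. A UK subject has no culture grade at Baseline or later, so that subject can never be recorded as having a lower grade. If the proportion is taken out of everyone in the group, such subjects sit in the denominator as if they had been graded and had not improved. The result then depends on how many subjects came from the UK as well as on what happened to the cultures.

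The second is the mismatch between variable and analysis. SAP 9.2.2 names time to positivity, while both summaries in SAP 9.3.2.4 use the grade alone. No table, figure, visit-level rule or change from Baseline is given for time to positivity there, in the changes listed in SAP 13, or in the interim analysis of SAP 14.

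The stake is modest but real. Bacterial load is a secondary objective, and protocol 6.3 says that the pilot is meant to inform the later phase II programme. A proportion that varies with the country mix is a poor input to that planning.

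**Working it through.** The plan gives no power, precision or expected value for this endpoint, so there is no figure to reproduce. The check is to trace the denominator and then show its effect over a range.

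**Which denominator applies.** SAP 3.1 would drop subjects with no grade, but it yields to any specific rule. SAP 9.3.2.4 contains a specific phrase, the number per group. Read literally, that phrase governs. A programmer could still follow SAP 3.1 together with SAP 12 and reach a different number. The text permits both.

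**Inputs.** Planned N = 30 (SAP 2.3). The split by country is not stated, so UK counts of 0, 5, 10 and 15 are assumed. The proportion of graded subjects with a decrease is assumed to be 40%.

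**Formulas.** Let N be all subjects, U the UK subjects and x the decreases, with x = 0.40 × (N − U).

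- Non-missing denominator: x / (N − U)
- Whole-group denominator: x / N = 0.40 × (1 − U/N)
- Highest attainable value on the whole-group denominator: (N − U) / N
- Exact (Clopper-Pearson) 95% limits on denominator n: the 0.025 quantile of Beta(x, n − x + 1) and the 0.975 quantile of Beta(x + 1, n − x)

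| UK of 30 | Graded | Decreases | Non-missing (95% CI) | Whole group (95% CI) | Ceiling |
|---|---|---|---|---|---|
| 0 | 30 | 12 | 40.0% (22.7–59.4) | 40.0% (22.7–59.4) | 100.0% |
| 5 | 25 | 10 | 40.0% (21.1–61.3) | 33.3% (17.3–52.8) | 83.3% |
| 10 | 20 | 8 | 40.0% (19.1–63.9) | 26.7% (12.3–45.9) | 66.7% |
| 15 | 15 | 6 | 40.0% (16.3–67.7) | 20.0% (7.7–38.6) | 50.0% |

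On the non-missing denominator the estimate stays at 40% and only the interval widens. On the whole-group denominator the estimate falls in proportion to the UK share, and the interval is too narrow because ungraded subjects count as information. With 15 UK subjects its width is 38.6 − 7.7 = 30.9 points, against 67.7 − 16.3 = 51.4 points for the subjects actually graded, and its upper limit lies below the assumed 40%.

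The same holds within a group. For an assumed group of 15 with 5 from the UK, 4 decreases give 4/10 = 40.0% (12.2–73.8) on the non-missing denominator and 4/15 = 26.7% (7.8–55.1) on the whole group.

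**Time to positivity.** SAP 9.2.2 names it and SAP 9.3.2.4 lists it per sample. The worst-of-visit rule in SAP 9.3.2.4 concerns grade. SAP 3.1 sets the format of continuous summaries but does not call for one here.

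**The case against.** The strongest reply is that the dilution is only one of two readings. Under SAP 3.1 and SAP 12, UK subjects drop out and the estimate is not biased. This stands in part. The literal text of SAP 9.3.2.4 favours the diluting reading, but the documents do not settle it, and the percentages above rest on assumed UK shares.

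A second reply is that the protocol endpoint is the grade, that the protocol never mentions time to positivity, and that the parenthesis in SAP 9.2.2 may merely describe how the grade is derived. Tabulating the grade does deliver the protocol endpoint. But if that is the meaning, SAP 9.2.2 should say so; as it stands, the named measure is not summarised.

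Two stronger readings are tempting.

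- A reader might infer that UK subjects are lost because time to positivity goes unsummarised, so that a summary would bring them back. The documents do not support this. UK subjects are missing because their laboratory supplies no grade, and SAP 9.3.2.4 names a source for time to detection only in the Australian transfer. Whether the UK transfer holds it is not stated.
- A reader might infer that the whole bacterial-load objective is answered in part of the sample. It is not. Table 4 of SAP 9.3.2.3 maps UK smear grades to the common scale, and UK subjects also contribute to culture conversion.

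Finally, this is a descriptive, uncontrolled pilot with no decision rule on this endpoint, and the SAP discloses the missing UK grade openly. That limits the weight of the point without answering it.

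**Conclusion.** The concern holds for the culture-grade endpoint. As literally written, the proportion with a decrease is biased down by a factor of (1 − UK share), where the share is unknown. For UK shares of one sixth to one half, an assumed 40% among graded subjects would read 33.3% to 20.0%. If SAP 3.1 is applied instead, there is no dilution, but the result describes Australian-laboratory subjects only, with a wider interval, and nothing in the planned outputs says so.

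This assumes that a UK change from positive to negative culture is not scored as a fall in grade. The SAP gives no rule for it, which is a further reason to write the denominator down.

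Separately, time to positivity is named as the measure and then only listed. Summarising it is a cheap addition for the Australian data. Any gain for UK subjects is unproven.

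**What to change.** In SAP 9.3.2.4:

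1. Set the denominator at each visit to subjects with a Baseline culture grade and a grade, or a negative culture, at that visit. Show that number in the table.
2. Label the grade table and the mean-change figure as Australian-laboratory (SNP) data, here and in the interim outputs of SAP 14.
3. Add a descriptive by-visit summary of time to detection, by laboratory and group. Include the UK laboratory only if its transfer contains the value, and state whether it does.
4. Treat cultures with no growth as censored at the laboratory's incubation limit. Neither document gives that limit, so it must be stated. Censoring avoids assigning a value, which would conflict with SAP 12.
5. Define Baseline for time to detection explicitly. SAP 3.3.3 pools Screening and the Baseline Visit and takes the worst result. Carried over to time to detection, that would compare the shortest time over two visits with the shortest time at one later visit, which favours apparent improvement. The rule should use like with like.
6. Align the parenthesis in SAP 9.2.2 with whatever is then analysed.

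The cost is SAP wording, one extra table and a smaller stated denominator. The Australian times are already to be extracted for the listing.
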